#### PCS Values for Vital Signs

Parameter	PCS Criteria
Systolic Blood Pressure	≤ 90 mmHg and a decrease of ≥ 30 mmHg from baseline* or ≥ 180 mmHg and an increase of ≥ 40 mmHg from baseline
Diastolic Blood Pressure	≤ 55 mmHg and a decrease of ≥ 20 mmHg from baseline or ≥ 90 mmHg and an increase of ≥ 30 mmHg from baseline
Pulse	≤ 50 bpm and a decrease of ≥ 30 bpm from baseline or ≥ 120 bpm and an increase of ≥ 30 bpm from baseline

#### 6.3.4 12-Lead ECG

Electrocardiograms will be performed at Screening, Visits 2, 4, 7, and 11. Only one assessment will be made at Screening, while assessments will be made in triplicate at later visits. All triplicate results will be averaged for summary and analysis purposes. Parameters to be summarized include: HR, PR, RR, QRS, QT, and QTc. The QTc interval will be presented by both the Bazett (QTcB = QT/(RR)1/2) and the Fridericia (QTcF = QT/(RR)1/3) corrections. For QTcF and QTcB at each study visit, the distribution of maximum values ( $\leq$  450, >450 -  $\leq$  480, >450 males, >470 females, >480 -  $\leq$  500, and >500 msec) as well as the distribution of the greatest change from Visit 2 (0 or less [no increase], 1-29 msec, 30-60 msec, > 60 msec, and >60 msec increase or >500 msec) will be presented. Appropriate visit windows for categorizing results will be established prior to database lock and unblinding.

When more than one value is available within a given visit window, the latest value will be used for tabulation purposes.

ECG results will be summarized by treatment group and visit. Descriptive statistics will include mean, 95% confidence interval, standard deviation, median, minimum, and maximum. Continuous ECG parameters will be summarized as change from Baseline (Visit 2). For the summary of change statistics, the Baseline mean and standard deviation will be provided for the subset of subjects with available data for the change summary. Clinical interpretations will also be summarized by visit and treatment group. Any ECG abnormalities, based on clinical interpretation, will be listed.

ECG results, including clinical interpretation and a flag for whether or not the value meets criteria for being possibly clinically significant, will be listed for all subjects.

## 6.3.5 Physical Exam

Complete physical examination is to be performed at Screening and, as needed in response to changes in medical history, at the final study visit (Visit 11, or earlier in the event of premature termination). The complete examination will consist of evaluation of the skin, head, eyes, ears, nose, throat, neck, thyroid, lungs, heart, lymph nodes, abdomen, and extremities. Brief, targeted physical examinations are to be performed at other visits as necessary in response to clinically significant adverse events.

[figure not shown]
Descriptive statistics will be provided for proportions of subjects with abnormalities on physical examination. Physical examination findings will be listed. These will be reviewed for any emergent abnormalities that could be attributed to the new dosage form.

## 6.3.6 Neurological Examinations

Neurological examination sufficient to establish the EDSS score is to be performed at Screening. The examination is to consist of an evaluation of mental status; corneal reflexes; extra-ocular movements; facial sensation (light touch); facial strength; palatal movement; tongue movements; neck extension; neck flexion; head turning; respiration; forced vital capacity; tendon reflexes of the right and left biceps, triceps, supinator, quadriceps, and ankle (scored as 0=absent, 1=reduced, 2=normal, 3=increased, 4=clonus); and plantar stimulation (scored as 0=no movement or flexor; 1=extensor). Targeted examination is to be repeated, as needed in response to changes in medical history, at the final study visit (Visit 11, or earlier in the event of premature termination).

Descriptive statistics will be provided for proportions of subjects with abnormalities on neurological examination. Neurological examination findings will be listed. These will be reviewed for any emergent abnormalities that could be attributed to the new dosage form.

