#### 10.4.5.6 Physical and Neurological Examinations

Descriptive statistics will be provided, by treatment group, for proportions of subjects with abnormalities on physical and neurological examinations. Physical and neurological examination

Confidential Page 61 of 67

findings will be listed. These will be reviewed for any emergent abnormalities that could be attributed to the new dosage form.

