#### 2. INTRODUCTION

This Statistical Analysis Plan (SAP) describes the planned statistical analyses to be performed for the analysis of data from Study CLR\_09\_21, "A Placebo-Controlled Randomized Withdrawal Evaluation of the Efficacy and Safety of

in Subjects with Spasticity Due to Multiple Sclerosis."

The SAP is prepared to provide a more technical and detailed elaboration of the principal statistical features stated in the protocol. The SAP will ensure that the tables, listings, and figures that will be produced and statistical methods that will be used are complete and accurate and will allow valid conclusions to be drawn. In the development of this SAP, the following documents were used:

- Protocol Number Version 7.0 Amendent 04, 16 Dec 2016
- Electronic Case Report Form (eCRF), 09 Mar 2012

The principles in the following guidance documents are followed in preparation of this SAP:

- International Conference on Harmonisation (ICH) E3 (1995): Structure and Content of Clinical Study Reports
- ICH E6 (1996): Guideline for Good Clinical Practice
- ICH E9 (1998): Statistical Principles for Clinical Trials

In the event that a discrepancy is found between the descriptions in the statistical section of the protocol and this document, the description in this document supersedes the descriptions in the statistical section of the protocol.

The responsible party at SPARC Ltd. will be required to review and approve all versions of the SAP.

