#### 3. STUDY OVERVIEW

## 3.1 Study Objectives

### 3.1.1 Primary Objectives

The primary objectives are to compare the continued treatment versus down-titration to placebo

• Demonstrating efficacy of spasticity

in the treatment of

- Indirectly demonstrating
- Determining the safety profile

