### 5.6 Final Reporting and Analysis

The randomization code will be broken at the end of the trial when all subjects have completed the study and only after all data have been entered into the database, cleaned, antispasticity medication use identified, and the database locked. Prior to the final unblinding, a review to identify the Per Protocol population will be undertaken. After database lock, the results will be analyzed and unblinded to the CRO statistician, programmer, and Sponsor.

All analyses outlined in the protocol and in this SAP will be carried out after:

- The SAP has been approved;
- The study database has been authorized by the study clinical team as complete and final;
- All analysis populations are determined;
- Treatment Failures have been identified; and
- Protocol deviations have been identified.

Further exploratory analyses not necessarily identified in this SAP may be performed to support the clinical development program. Any post hoc or unplanned analyses performed and not identified in this SAP will be clearly identified in the CSR.

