# 9.1 Planned Tables, Listings, and Figures

**Tables and Figures:** 

Tables and Figures	:
Table 14.1.1.1	Screen Failure Summary (All Subjects)
Table 14.1.1.2	Subject Disposition (All Subjects)
Table 14.1.2	Protocol Deviations Part 3 (ITT Population)
Table 14.1.3.1	Demographics and Baseline Characteristics (ITT Population)
Table 14.1.3.2	Demographics and Baseline Characteristics in Part 2 (Safety Population)
Table 14.1.3.3	Demographics and Baseline Characteristics in Part 3 (Safety Population)
Table 14.1.4	Medical History (Safety Population)
Table 14.1.5.1	Multiple Sclerosis History (ITT Population)
Table 14.1.5.2	Multiple Sclerosis History (Safety Population)
Table 14.1.6.1	Spasticity History (ITT Population)
Table 14.1.6.2	Spasticity History (Safety Population)
Table 14.1.7.1	Prior Medications (Safety Population)
Table 14.1.7.2.1	Concomitant Medications Part 2 (Safety Population)
Table 14.1.7.2.2	Concomitant Medications – Anti-Spasticity Part 2(Safety Population)
Table 14.1.7.2.3	Concomitant Medications – Neurological Part 2 (Safety Population)
Table 14.1.7.3.1	Concomitant Medications Part 3 (Safety Population)
Table 14.1.7.3.2	Concomitant Medications – Anti-Spasticity Part 3 (Safety Population)
Table 14.1.7.3.3	Concomitant Medications – Neurological Part 3 (Safety Population)
Table 14.1.8	Physical Examination Results (Safety Population)
Table 14.1.9	Neurological Examination Results (Safety Population)
Table 14.1.10.1.1	Exposure Dose Levels Parts 1 and 2 (Safety Population)
Table 14.1.10.1.2	Acceptable Conversion Dose Levels at Week 6 Parts 1 and 2 (Safety Population)
Table 14.1.10.1.3	Dosing Compliance Parts 1 and 2 (Safety Population)
Table 14.1.10.2.1	Exposure Dose Levels Part 3 (Safety Population)
Table 14.1.10.2.2	Dosing Compliance Part 3 (Safety Population)
Table 14.2.1	Treatment Failure Rates (ITT Population)
Table 14.2.2	Subject Global Impression of Severity (ITT Population)
14010 14.2.2	Subject Global Impression of Severity (11 1 1 optimizion)
Table 14.2.5	Treatment Failure Rates by Gender (ITT Population)
Table 14.2.6	Treatment Failure Rates by Race (ITT Population)
Table 14.2.7	Treatment Failure Rates by Age Group (<65 or ≥65) (ITT Population)

Table 14.2.20	Time To Dropout in Part 3 (ITT Population)
Table 14.3.1.1.1	Overview of Adverse Events in Part 2 (Safety Population)
Table 14.3.1.1.2	Incidence of Treatment-Emergent Adverse Events in Part 2 (Safety Population)

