Table 14.3.1.2.7	Incidence of Treatment-Emergent Adverse Events Leading to Discontinuation by Treatment Group in Part 3 (Safety Population)	
Table 14.3.1.2.8	Incidence of Treatment-Emergent Adverse Events by Gender by Treatment Group in Part 3 (Safety Population)	
Table 14.3.1.2.9	Incidence of Treatment-Emergent Adverse Events by Age Group by Treatment Group in Part 3 (Safety Population)	
Table 14.3.1.2.10	Incidence of Treatment-Emergent Adverse Events by Race by Treatment Group in Part 3 (Safety Population)	
Table 14.3.1.2.11	Incidence of Treatment-Emergent Adverse Events by Concomitant Medications in at Least 20% of Subjects by Treatment Group in Part 3 (Safety Population)	
Table 14.3.1.2.12	Incidence of Treatment-Emergent Adverse Events by Medical Conditions Present in at Least 20% of Subjects at Screening by Treatment Group in Part 3 (Safety Population)	
Table 14.3.1.2.13	Incidence of Treatment-Emergent Adverse Events by Renal function by Treatment Group in Part 3 (Safety Population)	
Table 14.3.1.2.14	Incidence of Treatment-Emergent Adverse Events by Dose at Earliest Onset by Treatment Group in Part 3 (Safety Population)	
Table 14.3.2.1.1	Incidence of Treatment-Emergent Serious Adverse Events in Part 2 (Safety Population)	
Table 14.3.2.1.2	Incidence of Treatment-Related Treatment-Emergent Serious Adverse Events by Highest Relationship in Part 2 (Safety Population)	
Table 14.3.2.1.3	Incidence of Fatal Treatment-Emergent Serious Adverse Events in Part 2 (Safety Population)	
Table 14.3.2.2.1	Incidence of Treatment Emergent Serious Adverse Events by Treatment Group in Part 3 (Safety Population)	
Table 14.3.2.2.2	Incidence of Treatment-Related Treatment-Emergent Serious Adverse Events by Highest Relationship in Part 3 (Safety Population)	
Table 14.3.2.2.3	Incidence of Fatal Treatment-Emergent Serious Adverse Events in Part 3 (Safety Population)	
Table 14.3.4.1.1	Vital Signs in Part 2 (Safety Population)	
Table 14.3.4.1.2	Vital Signs in Part 3 (Safety Population)	
Table 14.3.4.1.3	Potentially Clinically Significant Vital Signs in Part 2 (Safety Population)	
Table 14.3.4.1.4	Potentially Clinically Significant Vital Signs in Part 3 (Safety Population)	
Table 14.3.4.2.1	Hematology Laboratory Assessments (Safety Population)	
Table 14.3.4.2.2	Hematology Laboratory Shift Table (Safety Population)	
Table 14.3.4.2.3	Number and Percentage of Subjects with a Possibly Clinically Significant (PCS) Hematology Results – Safety Population	

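### SAP 6.3.5 and 6.3.6 omit the treatment-group split that protocol 10.4.5.6 requires for physical and neurological examination abnormalities, and Tables 14.1.8 and 14.1.9 do not restore it

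*SAP*

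**What the plan says.** Protocol 10.4.5.6 states: "Descriptive statistics will be provided, by treatment group, for proportions of subjects with abnormalities on physical and neurological examinations".

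The SAP covers the two examinations separately. Section 6.3.5 states: "Descriptive statistics will be provided for proportions of subjects with abnormalities on physical examination". Section 6.3.6 states: "Descriptive statistics will be provided for proportions of subjects with abnormalities on neurological examination". Neither sentence mentions treatment group or study part. Both sections add that the findings will be listed and reviewed for emergent abnormalities that might be due to the new dosage form.

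The planned-output list in SAP 9.1 has one table for each examination. Table 14.1.8 is titled "Physical Examination Results (Safety Population", with the bracket closing there, and Table 14.1.9 is its neurological counterpart. No Part 3 version of either is listed.

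On precedence, SAP section 2 says that where the protocol's statistical section and the SAP disagree, "the description in this document supersedes the descriptions in the statistical section of the protocol".

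**The concern.** Part 3 is the only randomized part of the study. SAP 3.1.1 opens "The primary objectives are to compare the continued treatment versus down-titration to placebo" and lists determining the safety profile among the purposes of that comparison. The protocol's treatment-group split is what makes the examination summary part of it.

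Followed literally, the SAP could produce a table in which results from the two randomized arms, and from subjects who left before randomization, appear in one column. Such a table would not show whether abnormalities were concentrated among subjects continuing the drug or among those tapered to placebo. It would do little for the dosage-form review that both SAP sections promise. At stake is a descriptive safety summary. The primary analysis, the significance level and the power are unaffected.

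**Working it through.** The point is textual and the plan gives no figure to reproduce, so the check sets the relevant passages side by side.

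1. **Is the omission real?** Protocol 10.4.5.6 names treatment group. SAP 6.3.5 and 6.3.6 carry the same commitment without it. Both SAP sentences are grammatically complete. A missing-figure marker stands before the one in 6.3.5, but nothing interrupts 6.3.6, so lost or blacked-out text does not explain an omission that occurs in both places.

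2. **Which document governs?** Protocol 10.4.5.6 lies in the protocol's statistical section, so the SAP's precedence rule covers it.

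3. **Does the table list restore the split?** Tables 14.1.8 and 14.1.9 name neither treatment group nor study part, and are set on the Safety Population. Under SAP 5.1 and 6.1.1 that population is formed at Visit 2, before randomization at Visit 7. It therefore includes subjects who leave during Part 2. On the planning figures (about 300 enrolled, at least 240 randomized) at most about 300 − 240 = 60 enrolled subjects would never be randomized. Fewer of these would be in the Safety Population, since some may leave during Part 1. SAP 5.1 defines a separate Safety Population for Part 3, but these two tables do not use it.

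4. **How are comparable safety data treated?**

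| Data | SAP text on treatment group | Part 3 table listed |
|---|---|---|
| Vital signs (6.3.3) | Yes, for Part 3 | Yes |
| ECG (6.3.4) | Yes | Yes |
| Part 3 adverse events (6.3.1) | Sentence on the layout breaks off | Yes; all 14 treatment-emergent event titles name treatment group |
| Laboratory tests (6.3.2) | No | No |
| Physical examination (6.3.5) | No | No |
| Neurological examination (6.3.6) | No | No |

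The laboratory case differs. Scheduled laboratory tests are at Screening and Visit 7, before double-blind dosing has had any effect. After Screening, the planned time point for the examinations is Visit 11 or early termination. For anyone in Part 3 this falls after randomization, so the arm is relevant.

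5. **What would a by-arm proportion rest on?** Under SAP 6.3.5 and 6.3.6 the final-visit examinations are repeated only as needed, when the medical history has changed, and targeted physical examinations at other visits follow clinically significant adverse events. SAP section 6 bases percentages on subjects with non-missing data. The denominator after randomization would therefore be the subjects examined, who are selected because something changed.

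**The case against.** The strongest reply is that the SAP is silent on the split and does not reject it. No sentence says the arms will be combined. SAP 5.6 says "All analyses outlined in the protocol and in this SAP will be carried out after" a list of conditions is met, which assumes that the protocol's analyses remain in the plan. SAP section 6 allows display by key variables where appropriate. Table titles are weak evidence of layout: Table 14.2.1, for the primary endpoint, does not name treatment group, nor do the Part 3 vital-signs and ECG tables, whose text requires it. Column layout belongs in the table shells, which are not in these documents.

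This disposes of one stronger reading. A reader might infer that the arms will be pooled, and the documents do not say so. But SAP 5.6 is mainly about timing, and section 6 permits a split without requiring one. For vital signs and ECG the SAP text supplies the treatment group and the title names Part 3. For the examinations neither does. The gap remains.

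A reader might also infer that findings could not be attributed to an arm. That goes too far. Listings 16.2.11 and 16.2.12 give each subject's findings, and Listing 16.1.7 gives the randomization. Protocol 9.2.1.2 sends new or changed conditions to the adverse event page, and Part 3 events are tabulated by treatment group. An emergent abnormality recorded as an adverse event would be visible by arm there. These routes do not replace the summary that the protocol specifies, but they limit the harm.

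Finally, a reader might extend the point to Table 14.3.2.2.3, "Incidence of Fatal Treatment-Emergent Serious Adverse Events in Part 3 (Safety Population", and to the related-event table before it, since neither title names treatment group. That rests on titles alone. Protocol 10.4.5.1 already requires Part 3 serious events by treatment group, and the matching SAP sentence in 6.3.1 breaks off where text is missing. It is not part of this point.

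**Conclusion.** The SAP drops the protocol's treatment-group split for the two examination summaries, its table list does not put it back, and its precedence rule favours the SAP wording. As written, the plan does not commit to a by-arm safety summary that the protocol specifies.

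The impact is low. It concerns descriptive output from examinations done only as needed after randomization, and the listings and by-arm adverse event tables cover much of the same ground. No numerical effect can be given, because the documents do not say how many subjects will be re-examined in either arm. The conclusion assumes that the unseen table shells do not already contain treatment-group columns. If they do, only the SAP text and table titles need aligning.

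**What to change.** In SAP 6.3.5 and 6.3.6, state that examination results after Visit 7 are summarized by treatment group on the Safety Population for Part 3, with the number of subjects examined in each arm shown and used as the denominator. Keep an overall summary for Screening and for subjects who leave before Visit 7. Split Tables 14.1.8 and 14.1.9 to match.

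The cost is a change of wording and of table columns, with no new data. The downsides are small cells in each arm and selection: subjects re-examined because their history changed do not represent their arm. A footnote should say so, and the proportions should not be read as arm-level rates of abnormality.

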# 6.3.7 Suicidality Assessments using C-SSRS

Frequencies of suicidal ideation and suicidal behavior at Baseline and during the trial (since last visit version) will be summarized.

## 7. TESTING/QUALITY CONTROL PLAN AND SOFTWARE/SYSTEM

All statistical programs will be written in SAS® version 9.3, or later. Statistical programs will be tested and reviewed for Quality Control (QC) by a second programmer/biostatistician not involved in the programming as per standard operating procedure (SOP). In addition, SOP will be followed to ensure that the information is complete, consistent, and accurately reflects the data stored in Clinical Data Management System (CDMS) database. Further all tables, figures, and listings (TFLs) will undergo a QC process by an independent biostatistician/programmer to ensure that the information is complete, consistent, and accurately reflects the data stored in CDMS.

## 7.1 Programming Specifications for TFLs

Appendix 1 provides a list of all the TFLs that are planned to be produced.

## 7.2 Formatting Conventions

The following formatting conventions will be used to output TFLs:

- TFLs are outputted by SAS Output Delivery System (ODS) into Rich Text Files (RTF) format.
- Tables and Listings will include borders around all headings and data cells.
- Output will be in landscape orientation with margins of 1.5 inches on top, and 1 inch for right, left, and bottom.
- The default font to be in tables/listings/figures will be Courier New.
- Preferred and minimum font size:

Portion of Output	Preferred	Minimum
Page Header	10 pt	8 pt
Title	10 pt	8 pt
Column header	10 pt	8 pt
Cells	10 pt	8 pt
Footnote	10 pt	8 pt
Page Footer	10 pt	8 pt

- Data will be centered within columns when the maximum length of the data being displayed is less than or equal to the maximum width of the column heading. When the maximum length of the data being displayed exceeds the maximum width of the column heading, the data will be left-justified.
- Column headings should be in initial capital characters. For numeric variables, include "unit" in the column heading when appropriate.
- In figures, axes will be labeled appropriately.

#### 7.3 Standard Text Conventions

#### 7.3.1 Header

All output (table, figure, or listing) will have the following header:

Sun Pharma Advanced Research Company Ltd.

Protocol CLR\_09\_21

Page xx of XX

All output will have the date and time (date and time output was generated) and internal page number in the footer. Tables/Figures/Listings should be internally paginated (i.e., page numbers should appear sequentially within each output).

#### 7.3.2 **Title**

At least three (3) lines, in general, will be reserved for the entire title.

- The first line is for the table/listing/figure number;
- The second line is for the actual title; and
- The third line is reserved for the analysis population descriptor.
  - Population(s) represented on the tables will be clearly identified in the last row of the table Title. Consistent terminology will be used to identify a population.
  - Sub-population(s) or special population(s) descriptions will provide sufficient detail to ensure comprehension of the population (e.g., ITT Subjects from Study Site 1, Per-Protocol Subjects from Study Site 2) used for analysis in a table, figure, or a data listing.

All titles will be centered, as shown in the following example:

